All subjects will also have standard, routine monitors placed by the treating team, including blood pressure, ECG, pulse oximetry, and EtCO2. Subjects will be randomized to either 1) receive oxygen by nasal mask (nCPAP) with CPAP of 10 mmHg or 2) standard oxygen therapy. Subjects randomized to nCPAP will have a nasal facemask (SuperNOVA) placed approximately 5 minutes prior to the procedural start. The mask attaches to the anesthesia circuit, oxygen flow will be set at 10 lpm, and the CPAP of 10 will be set by turning the "pop-off" valve to 10 mmHg. Subjects randomized to standard care will have oxygen delivered by nasal cannula or simple facemask with oxygen level set by the treating providers. The CPAP level of 10 will be chosen because previous studies suggest that 95% of airway obstruction can be alleviated with a CPAP of 7.1, and it is convenient marked on the anesthesia "pop-off" valve, ensuring standardization. For the CPAP group, flow below 10 lpm will be allowed in cases in which the patient or provider does not tolerate higher flows. For practicality, providers and patients will not be blinded to the intervention because application of the nasal mask is obvious. While the clinical team will have access to all of the routine monitors, they will be blinded to the research monitor data, which will include TcCO2 monitoring, respiratory volume monitoring (RVM), and BIS. Researchers analyzing the data will be blinded to the intervention.

All subjects will receive a routine propofol-based anesthetic per the treating clinical team. A study team member will record all airway maneuvers or interventions performed by the anesthesia team during the procedure, including changes in oxygen flow, ventilatory assistance, jaw thrust, or placement of an oral or nasal airway. Further, the duration of the endoscopic procedure and any anesthesia related interruptions will be recorded. The study duration will be entirely within the time period of the patients' visit to the endoscopy suite. All study monitors will be removed when the participants are discharged to home or transferred to the ward depending on the clinical routine or needs.

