Each subject will be assigned a study number to allow connection of the demographic data and clinical characteristics for comparison with the physiological data. All analog data for vital signs will be digitized using a digital to analog converter and processed using commercially available software. Medication data and length of stay data will be collected directly from EPIC .

Additionally, data relating to any respiratory events (decreased RR, oxygen saturation, airway obstruction, etc.) requiring intervention will be recorded. Raw data from the ExSpiron™ monitor, actigraph device, and transcutaneous monitor will be stored in a separate file with the file name being the study number assigned above. There will be no patient identifiers in these files.

a. Study duration and number of study visits required of research participants.

Enrollment and data collection will begin after IRB approval. For each subject, the study will be performed entirely within their visit to the endoscopy suite. No additional visits will be required of study participants.

b. Blinding, including justification for blinding or not blinding the trial, if applicable.

The clinical team will have access to all of the routine monitors, but they will be blinded to the research monitor data, which will include TcCO2 monitoring, respiratory volume monitoring (RVM), and BIS. For practicality, providers and patients will not be blinded to the intervention because application of the nasal mask is obvious. Researchers analyzing the data will be blinded to the intervention.

c. Justification of why participants will not receive routine care or will have current therapy stopped.

Except for the application of study monitors to the skin and nasal CPAP in the treatment group, all subjects will receive routine anesthesia care to facilitate the planned procedure. The procedure will not be effected by participation in the study.

d. Justification for inclusion of a placebo or non-treatment group. Not applicable

e. Definition of treatment failure or participant removal criteria.

If a case is aborted because of procedural problems and no anesthesia was provided or the duration of the procedure was too short to obtain data, the participant would meet criteria for removal from the study. However, if an anesthetic requires change to an alternate anesthesia plan (such as conversion to general anesthesia) this will be recorded in the analysis.

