## 7. Study Statistics

### a. Primary outcome variable.

The primary outcome will be the rate of hypoxia below 90% for  $\geq 15$  seconds.

- ### b. Secondary outcome variables. Secondary outcomes will include change in respiratory parameters (tidal volume, respiratory rate, minute ventilation, obstructive events), hypoventilation by TcCO2, EtCO2, and depth of anesthesia by BIS, as well as demographic differences. Demographic information to the occurrence of hypoxic events will be analyzed with logistic regression.

Statistical plan including sample size justification and interim data analysis.

Power analysis is based on a previous German study in the literature, of patients undergoing upper and lower endoscopy with hypoxia rates of 13.5% with standard care and 1.8% with application of nasopharyngeal airway. Using these figures to perform a power analysis for the primary outcome of hypoxia below 90%, with alpha 0.05 and power of 0.9, approximately 109 subjects in each arm or a total of 218 subjects will be needed. In order to obtain 109 completed subjects in each arm and to allow for those participants with incomplete datasets (e.g. monitor failure), we will enroll 120 subjects in each arm and a total of 240 subjects.

Frequency data will be analyzed with Fisher's Exact Test, ordered categorical data will be analyzed with the rank sum test, and continuous data will be analyzed with regression or equivalent techniques. Therefore, our primary outcome as to the incidence of hypoxia in each arm of the study will be determined using Fisher's exact test. All time series data from multiple sources will be aligned using the associated time stamp with the aid of the program data manipulation capabilities in Mathematica 11. Longitudinal analysis will be performed using a mixed model approach, initially with random intercepts alone, with the addition of nonlinear terms and interaction as indicated by the resulting model. Throughout, findings will be considered significant for  $p < 0.05$  and  $p$  values will be determined using two-sided tests. Statistical analysis will be performed with the aid of Stata 13. An analysis will be performed after the first 20 subjects to ensure complete data collection and to run a batched analysis of SCFA to evaluate this aim. An interim data analysis will be done after ~120 subjects have been enrolled.

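### Do the 109 completed subjects per arm and the removal of aborted cases turn the primary hypoxia comparison into a completer analysis?

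*Combined protocol and SAP*

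**What the plan says.** Section 7 defines the endpoint: "The primary outcome will be the rate of hypoxia below 90% for" at least 15 seconds. The arms are compared by a two-sided Fisher's exact test at 0.05. The sample size rests on "hypoxia rates of 13.5% with standard care and 1.8% with application of nasopharyngeal airway" with 90% power, which gives 109 per arm. Enrolment is then raised to 120 per arm, and the reason given is "In order to obtain 109 completed subjects in each arm and to allow for those participants with incomplete datasets (e.g. monitor failure").

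Section 4e allows removal of a participant whose case was "aborted because of procedural problems and no anesthesia was provided or the duration of the procedure was too short to obtain data". It gives no minimum duration. The same paragraph keeps cases that change to another anesthetic plan, such as general anesthesia, and has the change recorded in the analysis.

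Section 4 gives the source of the endpoint: "All subjects will also have standard, routine monitors placed by the treating team, including blood pressure, ECG, pulse oximetry" and end-tidal CO2. The research monitors (transcutaneous CO2, respiratory volume, BIS) are separate. On capture it says "All analog data for vital signs will be digitized". On blinding it says "providers and patients will not be blinded to the intervention because application of the nasal mask is obvious", and also "Researchers analyzing the data will be blinded to the intervention".

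The document does not name a primary analysis set, mention intention-to-treat, or give a rule for a missing primary outcome.

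**The concern.** Both statements about who counts point away from all randomised subjects: one speaks of completed subjects, the other of removal. The assigned mask goes on about 5 minutes before the procedure starts, so procedure length and data loss are known only after assignment, to staff who know the arm. Blinded analysts limit selective exclusion at the analysis stage, but not aborts or signal loss in the room. The endpoint needs only oximetry, so failure of a research monitor should not cost a subject, yet the term incomplete datasets does not separate the two kinds of failure.

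If sedated subjects who desaturated were removed more often from one arm, the risk difference would be biased. If losses were unrelated to hypoxia, the cost would be a little power.

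**Working it through.** **1. Reproduce the sample size.** Inputs from Section 7: p1 = 0.135, p2 = 0.018, two-sided alpha 0.05, power 0.90. The mean proportion is p̄ = 0.0765.

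Pooled formula: n = [1.960·√(2p̄(1−p̄)) + 1.282·√(p1(1−p1) + p2(1−p2))]² / (p1−p2)²

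= [1.960·0.3759 + 1.282·0.3667]² / 0.117² ≈ 106.4, so 107 per arm. The plan's 109 is within 2 subjects. Exact two-sided Fisher power at 109 per arm, by enumeration, is 0.908.

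**2. Read the step from 109 to 120.** 120 − 109 = 11, and 11/120 = 9.2%. Equivalently, 109/(1 − 11/120) = 120. This is an inflation for expected loss. It does not say who enters the test.

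**3. Power under either set.** Exact Fisher power is 0.908 at 109 per arm and 0.928 at 120 per arm.

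**4. How much selective loss would change the conclusion at the design rates?** The counts of lost events are assumptions, because the plan gives none. Completers at the planned rates: 15/109 vs 2/109, p = 0.0016. Now restore the 11 lost subjects in each arm.

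| Control events restored | CPAP events restored | Table | Fisher p |
|---|---|---|---|
| 0 | 3 | 15/120 vs 5/120 | 0.033 |
| 0 | 4 | 15/120 vs 6/120 | 0.066 |
| 1 | 4 | 16/120 vs 6/120 | 0.042 |
| 1 | 5 | 16/120 vs 7/120 | 0.078 |

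Significance is lost at 4 hidden CPAP events if no control event is restored, and at 5 if one is. If loss is unrelated to hypoxia, the chance of at least 5 events among 11 is about 8×10⁻⁷ at a rate of 1.8% and 0.010 at 13.5%. For at least 4 it is about 3×10⁻⁵ and 0.050.

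In the other direction, losing 7 control events (8/102 vs 2/109) gives p = 0.053. That error is towards no effect, not a false claim of benefit.

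**5. False-positive rate with no true effect.** Assume 13.5% in both arms, 120 per arm, each CPAP event dropped with probability f and no control event dropped. Exact enumeration:

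| f | Two-sided rejection rate |
|---|---|
| 0 | 3.1% |
| 0.1 | 4.3% |
| 0.2 | 6.8% |
| 0.3 | 11.6% |

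Fisher's test is conservative here, so losing a tenth of CPAP events still leaves the rate below 5%.

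**6. Set the removal rule against the endpoint.** The rule covers cases aborted for procedural problems. Its first limb (no anesthesia) removes subjects who had no sedation and so could not have the outcome. Its second limb (too short to yield data) describes subjects with no record to analyse. A sedated subject with a recorded desaturation has data and, on a plain reading, falls outside it. Conversions stay in. Section 5 admits only procedures expected to last more than 10 minutes, so very short cases should be uncommon, though no frequency is given.

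**The case for a change.** The strongest case for a change is that an inflated sample size does not define an analysis set, and whoever applies the too-short limb must decide case by case with no threshold. The sentence in Section 4e could even be read to cover any short procedure, not only an aborted one. In a borderline trial one removal matters: 16/120 vs 7/120 (p = 0.078) becomes 16/120 vs 6/119 (p = 0.042) if a single CPAP event is dropped. If all 11 per arm lacked oximetry, the worst case is 15/120 vs 13/120 (p = 0.84). Stating the set would cost only wording.

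The omission stands as a matter of fact. The consequence does not follow from it:

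- The borderline table was chosen to sit on the threshold, and the higher false-positive rates need 20% to 30% of CPAP events to vanish while every control event is kept. Nothing in the protocol points to losses of that kind.
- The worst case of 15/120 vs 13/120 assumes that the oximetry itself is missing. No definition of the analysis set can recover it.
- A criterion of at least 15 seconds needs a continuous, time-stamped oximetry record, not just a sensor. Monitor failure can therefore mean a missing primary outcome, and an allowance for it is proper.
- A written set of all randomised subjects who received sedation would largely repeat the first limb of Section 4e. It would differ only for sedated, aborted cases without data.

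**Conclusion.** The concern does not hold as a fault in the plan. The protocol omits a named primary analysis set and a threshold for too short, but it does not prescribe a completer comparison, and that reading is only an inference. The sensible reading is to test every randomised subject who was sedated and has usable oximetry, in the assigned arm and whatever the state of the research monitors, with an event before an abort counted. The text already allows this.

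The choice of set moves power by about 2 percentage points (90.8% to 92.8%). At the design rates the conclusion turns only on about 4 hidden CPAP events (no control event restored) or 5 (one restored) among 11. These figures assume 13.5% vs 1.8% and 11 lost per arm. The bias figures further assume losses tied to both arm and hypoxia, which the documents do not support. If the trial shows many removals, or unequal removals between arms, the point deserves another look when the results are read. It does not call for a change to the plan now.

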## **2. Objectives (include all primary and secondary objectives)**

Specific Aim 1: To test whether nasal CPAP reduces the incidence of hypoxia during procedural sedation with propofol as compared to usual care. Hypothesis: A randomized clinical trial of an intervention to reduce airway obstruction (nasal CPAP) will decrease the incidence of hypoxic events ( $<90\% \geq 15s$ ) compared to usual care in patients undergoing procedural sedation.

Specific Aim 2: To determine the duration, magnitude and mechanism of hypoventilation and its association with hypoxia in subjects undergoing procedural sedation. Hypothesis: By determining minute ventilation, transcutaneous CO2 and sedation depth while measuring end-tidal CO2, it will be possible to relate ventilation to hypoxic events, sedation depth and airway obstruction. Further, reductions in the incidence of hypoxia in the intervention group will be consistent with the hypothesis that loss of airway motor tone underlies hypoventilation and associated hypoxia.

Specific Aim 3: To characterize the physiologic state when end-tidal capnography is insufficient for detecting hypoventilation. Hypothesis: The amplitude of the capnographic signal is not representative of the adequacy of ventilation due to artifact from loss of airway motor tone during procedural sedation.

Specific Aim 4: To determine if there short chain fatty acid serum concentration is protective for procedural sedation induced hypoventilation, obstruction and hypoxia: Hypothesis: Higher concentration

of short chain fatty acids will be reduce the risk of hypoventilation, obstruction, and hypoxia and suggests a link between respiratory function and gut microbiome.

**3. Background** (briefly describe pre-clinical and clinical data, current experience with procedures, drug or device, and any other relevant information to justify the research)

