During general endotracheal anesthesia (GETA), airway obstruction is bypassed by the endotracheal tube and the closed system allows for minute ventilation to be continuously monitored and end tidal carbon dioxide (EtCO2) generally approximates arterial carbon dioxide (PaCO2). During monitored anesthesia care, end tidal carbon dioxide (EtCO2) monitoring is routinely utilized as a qualitative marker of respiratory rate, but quantitative evaluation to identify hypoventilation is usually not possible by nasal cannula or standard mask ("green mask). Likewise, minute ventilation is not routinely monitored. In fact, ETCO2 reading often decreases during hypoventilation with opioids and sedatives, while respiration paradoxically decreases (see figure, attached). Still, ETCO2 monitoring remains an important measure of respiratory rate, and has been shown to decrease the rate of hypoxia during procedural sedation for colonoscopy from 32% to 18%. Prevention of hypoxia by administering supplemental oxygen may blunt the potential increase in respiratory drive stimulated during opioid and sedative administration. However, prevention of hypoxia during procedural sedation using oxygen allows for airway interventions prior to the onset of hypoxia when ventilation is being carefully monitored. Current standard of care for monitored anesthesia care with sedation includes use of qualitative EtCO2 as a marker of respiration, but does not include quantitative monitoring of minute ventilation or the degree of hypoventilation.

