Impedance based respiratory volume monitoring has been used to assess adequacy of ventilation and airway obstruction in patients undergoing endoscopic gastrointestinal procedures. In fact, such studies also suggest that EtCO2 often decreases as minute ventilation decreases. In this study, changes in minute ventilation from baseline, and episodes of upper airway obstruction will be assessed using the commercially available ExSpiron™ (Exspiron, Respiratory Motion Inc, Waltham MA). Previous studies using the ExSpiron™ have suggested that decreased minute ventilation during sedation for GE procedures is primarily due to decreased tidal volume rather than respiratory rate. Transcutaneous carbon dioxide has proven to closely approximate to arterial carbon dioxide (PaCO2), and in fact more closely reflects PaCO2 than end tidal carbon dioxide (EtCO2). Transcutaneous carbon dioxide (TcCO2) has been shown to closely correlate with PaCO2. After approximately 5 minutes of calibration time, it appears to track changes in PaCO2 with a lag time of 30 seconds to 2 minutes. In our experience using the TcCO2 monitor

for clinical application during jet ventilation, we have found the device to consistently track within 5 points of the PaCO2. (Sentec, Therwil, Switzerland).

Depth of anesthesia using processed electroencephalography has been described as a marker for depth of anesthesia during GETA and MAC with sedation. Depth of anesthesia using bispectral index (BIS) has been relatively well established and is known to correlate well with other measures of depth of anesthesia. We will use bispectral index (BIS) (Medtronic, Minneapolis, Minnesota) as a marker of state. In addition, all clinical data utilized in routine practice will be recorded, including drug dosing, method of drug administration, and length of stay in the recovery area.

Recently, alterations in the gut microbiome have been implicated in obesity, hypertension, obstructive sleep apnea induced hypertension, and airway smooth muscle tone that may relate to reactive airway disease. In general, lower short chain fatty acid levels are associated with pathology, and higher levels appear to be

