This study is a randomized controlled trial comparing oxygen delivery by nasal mask with CPAP versus standard care (nasal cannula or standard facemask) during propofol-based sedation for GE procedures to reduce the incidence of hypoxia. The primary outcome will be the rate of oxygen desaturation below 90% for  $\geq 15$  seconds. In addition, secondary measures will include evaluation of mechanism and degree of respiratory depression associated with hypoxia and hypoventilation by characterizing changes in minute ventilation, tidal volume, and respiratory rate as well as the rate and degree of airway obstruction. We hypothesize that the addition of Nasal CPAP in the intervention arm will lead to decreased obstruction as positive pressure will stent open the obstructed airway. Depth of anesthesia will be monitored by BIS and we hypothesize that the degree of hypoventilation, obstruction, and will be significantly lower in the intervention arm compared to the control arm. Further, the depth of anesthesia will be independent of total propofol dose received. While the primary outcome in this study is hypoxia, we also seek to marry ETCO2 with minute ventilation and transcutaneous CO2 to better understand the total effects of sedation on respiration. Thus, the study will also serve to evaluate which mode(s) of respiratory monitoring might be the best possible intervention to enhance safety during procedural sedation. Further, we suspect that the amplitude of ETCO2 will not predict the degree of respiratory depression seen with other monitors. In addition, we will measure serum short chain fatty acid concentrations as a predictor and possible mechanism for differences in individual variability in anesthesia induced respiratory depression.

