All subjects enrolled in the study will have research monitors placed on the skin in a similar fashion to the pads for ekg lead placement, with respiratory volume monitoring on the chest, BIS and TcCO2 on the forehead. All enrolled subjects will be connected to the ExSpirom™ monitor (Respiratory Motion, Inc., Waltham MA) and digital respiratory traces of MV, TV, and RR measurements will be collected on all 240 patients. The ExSpirom monitor uses an adhesive, latexfree, adjustable 5 sensor strip applied to the chest to measure the amount of air moving in and out of the lung in real time. Minute ventilation will also be correlated to transcutaneous CO2 as measured by the SenTec Digital Monitor (SenTec AG, Therwil, Switzerland). Transcutaneous CO2 (Ptc CO2) monitoring provides a noninvasive technique allowing continuous monitoring of ventilation. It is based on arterialization of the capillary bed through the local application of heat and the use of Stow-Severinghaus electrodes. The sensor will be calibrated, applied to the patient's forehead, cheek, or chest, and warmed to a constant surface temperature of 42 °C. In adults, these temperatures are safe for up to 24h, and the procedures performed in this study are generally less than 2 hours. The BIS monitor is also an adhesive strip with 4 sensors applied to the subjects forehead.

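### Section 7 merges all signals by time stamp and names no TcCO2 lag, although the Background gives a delay of 30 seconds to 2 minutes, so within-subject TcCO2 associations would generally be attenuated

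*Combined protocol and SAP*

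**What the plan says.** Section 3 (Background) reports that, after about 5 minutes of calibration, TcCO2 appears to track PaCO2 "with a lag time of 30 seconds to 2 minutes". The delay is given against PaCO2 only.

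Section 7 (Study Statistics) has one merge rule: "All time series data from multiple sources will be aligned using the associated time stamp". The longitudinal analysis is a mixed model, "initially with random intercepts alone, with the addition of nonlinear terms and interaction as indicated by the resulting model". Neither that section nor any other names a shifted alignment, a cross-correlation or a lagged term.

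Several planned analyses put TcCO2 beside the other signals:
- Section 4: "Minute ventilation will also be correlated to transcutaneous" CO2.
- Section 2, Aim 2: from minute ventilation, TcCO2, sedation depth and EtCO2, "it will be possible to relate ventilation to hypoxic events, sedation depth and airway obstruction".
- Section 3: EtCO2 is to be combined "with minute ventilation and transcutaneous" CO2, partly to judge which monitoring mode is most useful.

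**The concern.** The plan states a sensor delay and then gives an alignment rule and a model that do not use it. If TcCO2 at a given second reflects arterial CO2 of 30 to 120 seconds earlier, pairing it with minute ventilation at that same second compares two different physiological moments. The usual result is a correlation or slope that is too small. The planned correlation of minute ventilation with TcCO2, and the Aim 2 links that use TcCO2, could then look weaker than they are. TcCO2 could also look less informative than other monitors because it is read late. In Aim 3, some disagreement between EtCO2 and TcCO2 could be sensor delay rather than failure of capnography.

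**Working it through.** **Inputs from the documents.** TcCO2 lag behind PaCO2: 30 to 120 s (section 3). Alignment and model: section 7. Procedures: longer than 10 minutes (section 5), generally under 2 hours (section 4). A 120 s lag is therefore under 120/600 = 20% of an eligible procedure, and 120/7200 = 1.7% of a 2-hour one.

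**Assumptions, because the documents give no signal dynamics.** Each signal has autocorrelation exp(-h/tau), with tau = 60, 300 or 600 s. In steps 2, 4 and 5 the other signals have no delay of their own.

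**1. The plan's own figure.** The only design calculation is 109 per arm. The pooled two-proportion formula with 13.5% against 1.8%, two-sided alpha 0.05 and power 0.90 gives [1.960 x sqrt(2 x 0.0765 x 0.9235) + 1.282 x sqrt(0.1168 + 0.0177)]^2 / 0.117^2 = 106.4, so 107. Power at 109 per arm is 0.907. The figure reproduces, and TcCO2 plays no part in it.

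**2. Same-stamp correlation as a share of the lag-matched one.** For a pure shift L the share is exp(-L/tau). For a gradual first-order response with time constant T it is sqrt(tau/(tau+T)).

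| Case | tau 60 s | tau 300 s | tau 600 s |
|---|---|---|---|
| Shift 10 s | 0.85 | 0.97 | 0.98 |
| Shift 30 s | 0.61 | 0.90 | 0.95 |
| Shift 120 s | 0.14 | 0.67 | 0.82 |
| First-order, T = 30 s | 0.82 | 0.95 | 0.98 |
| First-order, T = 120 s | 0.58 | 0.85 | 0.91 |

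**3. Simulated within-subject slopes.** The setting was 240 subjects, 30-minute records, sampling every 5 s and subject-mean centring. Minute-ventilation time constants were 1, 2, 5 and 10 minutes. PaCO2 followed ventilation either at once or with an assumed 3-minute response. Ratio of same-stamp to lag-matched slope:

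| Lag | PaCO2 at once (1, 2, 5, 10 min) | 3-min PaCO2 response (1, 2, 5, 10 min) |
|---|---|---|
| 0.5 min | 0.58, 0.75, 0.87, 0.91 | 0.49, 0.70, 0.85, 0.88 |
| 1 min | 0.32, 0.56, 0.76, 0.83 | 0.17, 0.46, 0.70, 0.78 |
| 2 min | 0.08, 0.29, 0.54, 0.67 | -0.05, 0.12, 0.44, 0.62 |

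The same-stamp slope was smaller in size in all 24 scenarios. Several ratios fall below step 2 (0.67 against 0.82 at 2 minutes and a 10-minute time constant), because centring short records removes slow variation. There are exceptions to the rule. A pure linear trend is not attenuated (ratio 1.00). A 4-minute cycle with a 2-minute lag reverses sign without shrinking.

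**4. EtCO2 against TcCO2.** As an illustration (not a planned endpoint), the share of time that two Gaussian signals spend on opposite sides of their means is arccos(r)/pi. For shifts of 30 to 120 s at tau 60, 300 and 600 s:
- Exact tracking plus delay, r = exp(-L/tau): 29-46%, 14-27% and 10-19%.
- Exact inverse relation plus delay: 71-54%, 86-73% and 90-81%.
- True correlation 0.5, no delay: 33%, which lies inside the first range at tau 60 s.

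**5. Which lags to cover.** With lags of 0, 30, 60, 90 and 120 s entered together, the worst-case multiple R over net lags of 0 to 120 s is 0.87, 0.98 and 0.99. Minute ventilation may need more, because any delay from ventilation to PaCO2 adds to the sensor lag. For a first-order PaCO2 response with rate a = 1/180 s and a ventilation signal with rate b = 1/tau, the correlation peaks ln[2a/(a+b)]/(a-b) after the sensor lag. That is 62, 100 and 111 s. Adding 120 s gives about 182, 220 and 231 s, beyond a 120 s grid but inside 240 s.

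**6. How to test.** Independent signals were simulated for 218 subjects, with 30-minute records every 10 s.
- Taking the smallest of five fixed-lag p values gave 8-12% false positives against a nominal 5%.
- A five-term joint test with independent residuals, approximating random intercepts alone, rejected in 62-80% of trials in one run and about 63-78% in another.
- Subject-clustered standard errors gave 5-7%.

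**The case against.** The strongest reply is that the defect is inferred. Time-stamp merging is a step that any lag analysis also needs, and section 7 leaves room for model building and for other regression techniques. The correlation in section 4 is not said to be within-subject or same-stamp; it could be done on per-subject or per-episode summaries, which a short lag barely touches. The size rests on time constants that the plan does not give, and slow signals lose little.

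Much of this stands. A reader might infer that the plan commits to lag-zero pairing, but it does not. A reader might also take 30 to 120 s as the delay against every signal. The documents give it against PaCO2 only, so the net lag may be under 30 s for some signals and over 120 s for minute ventilation.

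What does not stand is that this is only missing detail. The plan describes time-aligned series and a longitudinal model, states a delay, and names no step that uses it. Leaving the lag to be settled after the data are seen also invites choosing it by p value (step 6).

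**Conclusion.** The concern holds, as a limited point. Followed as written, same-stamp within-subject associations of TcCO2 with minute ventilation, EtCO2, BIS or SpO2 would generally be attenuated. The share of the correlation kept runs from 0.95 down to 0.14 for a 30-120 s pure shift with assumed time constants of 600 down to 60 s. The loss is milder if the response is gradual or the net lag is short. The direction is well supported; the size is not known.

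A reader might go further and infer that the delay undermines the trial's main result or Aim 3. The documents do not support that. The primary Fisher test, the sample size, per-subject or between-arm TcCO2 summaries, and EtCO2 against minute ventilation are not shown to be affected. Section 3 expects that the EtCO2 "reading often decreases during hypoventilation with opioids and sedatives", and a strong inverse relation to TcCO2 would still show: under the model in step 4, delay alone never pushes discordance above 50%. Confusion is likely mainly where the EtCO2-TcCO2 association is weak or intermediate. What is at stake is the secondary mechanistic work in Aim 2 and the TcCO2 part of Aim 3.

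**What to change.** Add one pre-specified analysis to section 7:

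> After merging by time stamp, within-subject analyses involving TcCO2 enter TcCO2 read at 0, 30, 60, 90 and 120 s after the other signal, extended to 240 s when the other signal is minute ventilation, as distributed-lag terms with one joint test using subject-clustered standard errors or a serially correlated residual structure. The association at each lag, including lag 0, is reported descriptively, and no lag is chosen by its p value. Airway maneuvers falling within the lag window are flagged, and results are repeated without those windows.

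The direction must be explicit. Reading TcCO2 60 s earlier instead would lower the pure-shift multiplier to exp(-(L+60)/tau), which is 0.22-0.05 at tau 60 s. The flag on maneuvers matters because later readings can follow an intervention. Section 4 already provides that "A study team member will record all airway maneuvers or interventions performed by the anesthesia team during the procedure", but flagging also needs the time of each one.

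The cost is one paragraph and a few lines of code. Raw transcutaneous data are already stored and monitors stay on until discharge or transfer (section 4), so later readings should exist. The downsides are a little more analysis and reporting, collinear lag terms whose single coefficients are imprecise, and a true lag that stays uncertain in each patient.
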